PPMC	Penn Presbyterian Medical Center

1 STUDY SUMMARY

1.1 Synopsis

Title:	Airalux Digital Incentive Spirometer
Short Title:	Digital Incentive Spirometer
Study Description:	This single-arm proof-of-concept research study aims to assess the effect of a digital incentive spirometer (IS) device and a companion mobile-based app on incentive spirometry adherence in patients post-surgery. The digital IS utilizes a sensor to measure inspiratory breaths, and these data are transmitted wirelessly to a secure cloud database. The spirometer and app include a patient reminder system, exercise gamification strategies, progress tracking, and additional features designed to promote patient IS use.
Objectives:	The objective of this study is to evaluate the effect of a digital IS that provides gentle auditory and haptic reminders and exercise guidance on patient adherence to incentive spirometry. Secondarily, this study will evaluate metrics relating to lung function to assess post-surgery lung recovery in patients using the digital IS.
Primary Endpoint:	Total incentive spirometry adherence - Number of inspiratory breath attempts performed with the digital IS per day. Consistency of incentive spirometry adherence throughout postoperative stay - Percent of recorded hours in which at least one inspiratory breath was attempted using the digital IS.
Secondary Endpoints	Quality of inspiratory breaths attempted with the digital IS - quality refers to inspiratory volumes achieved. Blood oxygen saturation - Postoperative SpO2 Pain Scores - Postoperative pain scores will be reported on a scale from 0 (no pain) to 10 (unbearable pain). Pulmonary function testing lab results – preoperative spirometry results from pulmonary function lab

Study Population:	
30 patients (of adult categorization) undergoing anatomic lung resection surgery and receive an incentive spirometer as standard-of-care. No restriction on gender, demographic group, or geographic location.
 
We will be enrolling patients that receive surgery from [name] (Principal Investigator), [name] (Chief of Thoracic Surgery), and/or [name] (Chief of Surgery, PPMC) at the sites listed below.

Phase:	Exploratory
Description of Sites/Facilities	
Hospital of the University of Pennsylvania, [name]
 
Penn Medicine Valley Forge, [name]
 
Penn Medicine University City, [name]
 
Penn Medicine Cherry Hill, [name]
 
Penn Thoracic Surgery Presbyterian, Presbyterian Medical Center of the University of Pennsylvania, [name]
 
Perelman Center for Advanced Medicine, [name]

Enrolling Sites:	
Hospital of the University of Pennsylvania, [name]
 
Penn Medicine Valley Forge, [name]
 
Penn Medicine University City, [name]
 
Penn Medicine Cherry Hill, [name]
 
Penn Thoracic Surgery Presbyterian, Presbyterian Medical Center of the University of Pennsylvania, [name]
 
Perelman Center for Advanced Medicine, [name]

Description of Study Intervention:	
Patients will be instructed to periodically perform inspiratory breaths from the mouthpiece of the digital IS device during their postoperative stay similar to how standard-of-care incentive spirometers are instructed. The digital IS utilizes a sensor to measure inspiratory flow rates and volumes. These data will be displayed to the patient during inspiratory breaths on the device screen. The screen and a speaker in the device along with the mobile

	app will provide visual and auditory cues to guide patients in performing inspiratory breaths and periodically remind patients to perform them.
Study Duration:	Estimated length of time to enroll all subjects and complete the study: 3 months.
Participant Duration:	For the entirety of a patient's postoperative hospital stay until they are discharged (on average 2-3 days) or up to 1 week post-surgery.

1.2 Key Roles and Study Governance

Sponsor	Medical Director
N/A, principal investigator-initiated study	[name]
	Division of Thoracic Surgery, Hospital of the University of Pennsylvania
	[name]
	[contact]
	[contact]

- 1.3 Schema

Office (within 1-30 days prior to surgery) - Informed Consent

- Obtain informed consent alongside surgery consent
- (Optional) Obtain patient or family member email address (linked to their Apple ID) to approve access to the Airalux app on their App Store (IOS only)
 - The Airalux app provides guided IS exercise sessions, allows patients and family members to view past IS exercise measurements, and gamifies adherence metrics.

Pulmonary function lab – Spirometry Testing

- Patients will receive spirometry testing at the pulmonary function lab. This is part of routine care. This is not a study intervention.

Pre-op holding (morning of surgery) - Baseline Measurement

- Patients receive the Airalux device and use it to perform a baseline IS measurement
- Research team records the device identification key of the device that the patient is receiving
- (Optional) For patients with the Airalux app, they can sign in to the app with their device identification key.

Post-anesthesia care unit (2-4 hours post-surgery) - Study Intervention Administered

- Patients are instructed to perform IS exercises with their device
- The device will gently vibrate/buzz every 15 minutes to prompt patients to complete an IS exercise
- (Optional) Patients can follow guided exercises on the app if desired

Inpatient hospital floor (0-7 days post-surgery) - Study Intervention Administered, Collection of Endpoints

- Patients are instructed to perform IS exercises with their device throughout their hospital stay
- The device will vibrate every 15 minutes to prompt patients to complete IS exercise
- (Optional) Patients can follow guided exercises on the app if desired
- Patient pulse oximetry data is collected every 4 hours. This is part of routine care. This is not a study intervention.
- Patient pain scores are collected at minimum every 12 hours (at least once per shift). This is part of routine care. This is not a study intervention.

Discharge - Study Ends (conclusion of hospital stay)

- Patients will not be able to use the Airalux device outside of the hospital
- Patients will receive a standard of care incentive spirometer to use at home
- Patients will complete a survey on their experience with using the device

2 INTRODUCTION AND RATIONALE

2.1 Study Rationale

Incentive spirometry is frequently prescribed as a standard-of-care for patients post-surgery to reduce the risk of developing postoperative pulmonary complications associated with atelectasis. An incentive spirometer (IS) is a mechanical breathing device that assists with pulmonary rehabilitation through improving lung expansion by encouraging deep breathing. While performing incentive spirometry exercises is effective at lowering atelectasis severity, ventilation time, and pulmonary complication rates, patient adherence to performing exercises is very poor. Medical staff, due to time constraints, often cannot supervise all of their patients' entire incentive spirometry regimens (usually every 10-15 min during wakeful hours), contributing to low adherence and incorrect exercise completion. This is compounded by current incentive spirometers lacking a method for accurately collecting patient exercise and adherence data. The present study seeks to evaluate the effect of a digital IS that provides instruction signals and exercise reminders on patients' incentive spirometry adherence.

2.3 Risk/Benefit Assessment

2.3.1 *Known Potential Risks*

The digital IS is a lightweight, handheld device that poses no significant risk to the patient. The 2 main components of the device (the main device body and the mouthpiece) are both large enough such that they pose a very low risk for choking. All electronic components are housed inside the device and are electrically insulated.

2.3.2 *Known Potential Benefits*

We do not claim any immediate potential benefits to the patient. Long-term benefits would be contributing to a study that would determine the efficacy of a digital IS device on incentive spirometry adherence, which may correlate with positive post-surgery clinical outcomes.

2.3.3 *Assessment of Potential Risks and Benefits*

The risks discussed above are minimal and non-significant. The benefits of participating in the study and contributing to the evaluation of a digital IS device that may improve incentive spirometry adherence and post-surgery outcomes outweighs these risks.

3 STUDY OBJECTIVES AND ENDPOINTS

OBJECTIVES	ENDPOINTS	JUSTIFICATION FOR ENDPOINTS
Primary		
The primary objective is to evaluate the effect of a multifeatured digital IS and integrated phone app on patient adherence to incentive spirometry. Together the device and app will include the following functions: an auditory and haptic reminder cue, visual and auditory cues to guide exercise completion, exercise gamification, and data tracking and visualization features.	The primary endpoints are totality and consistency of incentive spirometry adherence. Specifically, total adherence is a measure of the number of inspiratory breath attempts performed with the digital IS per day, and the consistency of adherence is a measure of the percent of hours in which at least one inspiratory breath was attempted using the digital IS.	The number and frequency of inspiratory breath attempts with the digital IS will be evaluated to assess patient adherence to incentive spirometry.
Secondary		
The secondary objective is to evaluate metrics relating to lung function to assess post-surgery lung recovery in patients using the digital IS.	The secondary endpoints are postoperative blood oxygen saturation (SpO ₂), postoperative pain scores, preoperative pulmonary function spirometry results, and postoperative inspiratory breath quality. Pain scores will be on a scale from 0 (no pain) to 10 (unbearable pain). Specifically, quality refers to inspiratory volumes achieved over time and the flow rate at which inspiratory breaths were taken.	Blood oxygen saturation, pain scores, preoperative spirometry results, and inspiratory breath quality will be evaluated to assess post-surgery lung recovery in patients using the digital IS.
Tertiary		
The tertiary object is to evaluate patient user experience of the digital IS device.	A tertiary endpoint will be survey responses collected from patients at discharge. Please see attached survey for survey questions.	These will be used to assess user experience of the device and companion app if applicable.

4 STUDY PLAN

4.1 Study Design

We hypothesize that use of the investigational device will have a positive impact on patient incentive spirometry adherence. This is a single-arm, exploratory study that will be conducted at the Hospital of the University of Pennsylvania (HUP) and Penn Presbyterian Medical Center (PPMC). The digital IS utilizes a sensor to measure inspiratory breath volume and flow rates, and this data, as well as the time stamps, are transmitted wirelessly to a secure cloud database and a companion mobile-based app. The IS and app incorporate features to instruct and remind patients about their exercises, which include auditory and visual cues as well as a gentle auditory and haptic reminder to perform exercises. Furthermore, the app has additional features to encourage breathing exercises in the form of gamification strategies, and separate interfaces for patients and medical staff to monitor device usage. All of the features are aimed at improving patients' adherence to incentive spirometry.

Subjects will be recruited from patients undergoing any lung resection surgery performed by [name], [name], and/or [name] at HUP and/or PPMC and for which an incentive spirometer is expected to be used by the patient after their surgery. The target enrollment for the study is 30 subjects. The duration of the subject's participation with the trial will be for their entire postoperative hospital stay up to 1 week postoperatively. At the beginning of the subject's participation, study activities will be focused on informed consent, instruction on use of the digital IS, and obtaining baseline inspiratory volume measurements. Most of the remainder of the subject's participation time will be focused on passive data collection performed by the digital IS.

4.2 Scientific Rationale for Study Design

The purpose of this exploratory study is to evaluate the effect of an investigational device on incentive spirometry adherence.

4.3 End of Study Definition

A participant is considered to have completed the study if he or she has completed all phases of the study including the last visit or the last scheduled procedure shown in the Schedule of Activities (SoA), Appendix Section 12.1.

5 STUDY POPULATION

5.1 Inclusion Criteria

To be eligible to participate in this study, an individual must meet all of the following criteria:

1. Provision of signed and dated informed consent form

2. Stated willingness to comply with all study procedures and availability for the duration of the study
3. Male or female, 18 years or older.
4. Undergoes any anatomic lung resection surgery
5. An incentive spirometer is expected to be ordered for the patient as standard-of-care
6. There is no restriction on active medications.

5.2 Exclusion Criteria

There are no exclusions based on economic status, gender, race, or ethnicity. An individual who meets any of the following criteria will be excluded from participation in this study:

1. Vulnerable populations who in the opinion of the investigator are unable to give Informed Consent for reasons of incapacity, immaturity, adverse personal circumstances or lack of autonomy.
2. History of prior non-compliance to prescribed therapy or presence or history of significant psychiatric condition (e.g., drug or alcohol addiction, psychosis, schizophrenia), or cognitive issue which would in the opinion of the investigator, make it difficult for the patient to comply with the study procedures or follow the investigators instructions.
3. Populations for whom in the opinion of the investigator, incentive spirometry is deemed inappropriate due to medical condition or otherwise.
4. Pregnant individuals due to low likelihood of meeting inclusion criteria 4 in section 5.1.

Licensed medical professionals on the clinical team will follow proper procedures in determining if the individual is consenting. Proper procedures entail doing all of the following: giving a patient adequate information concerning the study, providing adequate opportunity for the patient to consider all options, responding to the patient's questions, ensuring that the patient has comprehended this information, obtaining the patient's voluntary agreement to participate and, continuing to provide information as the patient or situation requires. There will be ample opportunity for the patient to ask questions. In the event that the patient is in a vulnerable population and unable to provide consent, they will not be eligible to participate in the study and thus will not be screened. If the individual is not able to provide informed consent or if consent is not certain due to impairments or other factors, they will not be considered for study participation. In the event that the patient is in a vulnerable population and unable to provide consent, they will not be eligible to participate in the study and thus will not be screened.

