6.3 Measures to Minimize Bias: Randomization and Blinding

This is a single-arm exploratory study which will not require participant randomization or blinding.

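### Excluding patients with past non-compliance removes likely low adherers from a single-arm adherence study, so its mean may overstate adherence in lung-resection patients generally

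*Combined protocol and SAP*

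**What the plan says.** Section 5.2, exclusion 2, opens with "History of prior non-compliance to prescribed therapy or presence or history of significant psychiatric condition", continues to cognitive issues, and ends with a qualifier: "which would in the opinion of the investigator, make it difficult for the patient to comply with the study procedures". The grammar leaves open whether the qualifier governs the non-compliance limb ("History of prior non-compliance to prescribed therapy") or only the conditions that follow it. Section 5.1, inclusion 2, also asks for "Stated willingness to comply with all study procedures and availability for the duration of the study".

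Section 3 states: "The primary objective is to evaluate the effect of a multifeatured digital IS and integrated phone app on patient adherence to incentive spirometry". It adds: "The primary endpoints are totality and consistency of incentive spirometry adherence". These are measured as breath attempts per day and the percent of hours with at least one attempt. The synopsis (section 1.1) describes the aim as an effect "on incentive spirometry adherence in patients post-surgery", with no limit to patients who have complied in the past. Section 4.1 hypothesises a positive impact on adherence.

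Section 6.3 says: "This is a single-arm exploratory study which will not require participant randomization or blinding". Section 9.4.2 plans a mean and standard deviation only. No section gives a reason for the non-compliance limb.

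**The concern.** Sections 2.1 and 2.2 justify the device by poor adherence, which surveyed providers attribute mainly to forgetting. A patient known not to follow prescribed therapy is one in whom a reminder device might be informative, and also one likely to lower the mean. Exclusion 2 leaves such patients out. With no control arm, no internal comparison can cancel the effect of who was let in.

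What is at stake is the level of adherence reported and the population it describes. If the mean is read as what lung-resection patients do when given this device, it may be too high.

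**Working it through.** **Is the limb needed?** Three passages bear on this.

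- Section 2.3 calls the risks minimal, so safety does not supply a reason.
- Section 8.1 leaves patients free to decide when and how often to use the device. Low use is therefore a legitimate value of the endpoint, not a failure of the protocol.
- The psychiatric and cognitive clause already covers patients who cannot follow instructions.

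**Does the qualifier help?** If it governs only the later conditions, any history of non-compliance excludes. If it governs the whole criterion, the investigator excludes past non-compliers who are expected to struggle with the study procedures. The main procedure is the exercise that forms the endpoint, so this reading ties the selection more closely to the endpoint.

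**Could the selection be measured afterwards?** Section 5.4 defines screen failures as people who consented but were not then evaluated with the device. Section 8.1 has the clinical team check eligibility when a patient is identified, and leaves only criteria missing from the chart until after consent. Patients excluded at the first step are not counted.

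**Direction and size.** The plan has no figure of its own to reproduce: section 9.1 states no hypothesis, and section 9.2 bases the 30 patients on expected case numbers. Take a two-group mixture:

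- q = share of otherwise eligible patients excluded by this limb (assumed; not in the documents)
- r = their mean adherence relative to enrolled patients (assumed; not in the documents)

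Set the enrolled mean to 1. The mean over all otherwise eligible patients is (1 − q) + q·r = 1 − q(1 − r), so

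overstatement = 1 / (1 − q(1 − r)) − 1.

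| q | r = 0.7 | r = 0.5 |
|---|---|---|
| 10% | 1/0.97 − 1 = 3.1% | 1/0.95 − 1 = 5.3% |
| 20% | 1/0.94 − 1 = 6.4% | 1/0.90 − 1 = 11.1% |
| 30% | 1/0.91 − 1 = 9.9% | 1/0.85 − 1 = 17.6% |

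Wider assumptions run from 0.5% (q = 5%, r = 0.9) to 29% (q = 30%, r = 0.25). The overstatement is zero if q = 0 or r = 1.

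**Scale checks.**

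- The reminder trial cited in section 2.2 reports 35.4 against 17.1 daily exercises, a ratio of 2.07. For selection alone to produce that ratio, q(1 − r) would have to be 1 − 1/2.07 = 0.52. This exclusion is unlikely to do so.
- With 30 patients, the 95% interval for a mean has a half-width of 2.045/√30 = 0.37 SD. At assumed between-patient coefficients of variation of 25%, 50% and 100%, that is about 9%, 19% and 37% of the mean. The possible shift is of the same order as the imprecision or smaller, but more precision would not remove it.

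**The case against.** Several points on the other side stand and limit the claim.

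- A reader might infer that the trial selects on its own outcome. It does not. The criterion concerns past compliance with prescribed therapy in general; the endpoint is postoperative device use recorded after enrolment. The documents give no data linking the two.
- A reader might infer that the primary estimate is biased outright. For the population the criteria define, it is not. Section 9.4.2 plans no comparison, so the issue is how far the mean generalises. It still matters because sections 1.1 and 4.1 speak of an effect on adherence in post-surgery patients without that restriction.
- A reader might infer that comparison with the cited 17.1 per day would credit the device with the selection. No such comparison is planned. The figure comes from cardiac surgery, and that trial's eligibility rules are not in the documents.
- A reader might infer that the result would not apply to the patients who need the device. Section 2.2 presents poor adherence as widespread (86% of surveyed providers agree) and forgetting as its most cited reason (83.5% of respondents). On that account, patients with no record of non-compliance need reminders too.

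It is also fair to say that deleting the limb does not remove all selection. Inclusion 2 remains, as does the clause on difficulty complying. Section 7.1 treats data from patients who discontinue as of no use for analysis, and section 7.2 does not replace those who received the device, so newly admitted patients who stop could still drop out of the mean. This argues for pairing the deletion with a rule on their data. It does not make the deletion pointless.

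**Conclusion.** The point holds as one of generalisability, and it merits a cheap change to the plan. Exclusion 2 removes patients on a likely predictor of both primary endpoints, without a stated reason, from a single-arm study framed for post-surgery patients generally. The direction rests on one assumption: that past non-compliers adhere less on average. Under it, the enrolled mean overstates adherence among all lung-resection patients given a spirometer. The range of about 3% to 18% is illustrative, since neither input is in the documents. The study is exploratory and the likely shift is modest, so this does not undermine it. It does limit what the mean can be said to describe.

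**What to change.** Delete "History of prior non-compliance to prescribed therapy" and the "or" that follows it from exclusion 2. Keep the psychiatric and cognitive clause for patients unable to follow instructions. In sections 7.1 and 9.4, state that the adherence data of low users and early stoppers stay in the primary analysis, so that the selection does not return at that stage.

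If the sponsor keeps the limb, give the reason, count every patient excluded under it, including those excluded on chart review before consent, and limit the conclusion to patients without prior non-compliance.

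The cost is a minor eligibility amendment, best made before enrolment because excluded patients cannot be recovered later. The recruitment pool widens slightly. The downside is that observed adherence may be lower and a few more patients may stop using the device.

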5.3 Lifestyle Considerations

Not applicable.

5.4 Screen Failures

Screen failures are defined as participants who consent to participate in the study but are not subsequently evaluated with the investigational device. A minimal set of screen failure information is required to ensure transparent reporting of screen failure participants, to meet the Consolidated Standards of Reporting Trials (CONSORT) publishing requirements and to

respond to queries from regulatory authorities. Minimal information includes demography, screen failure details, eligibility criteria, and any serious adverse event (SAE).

